7.3.1.1.3 Criteria for Stopping the DBPCFC

The instructions for each of the DBPCFCs during the double-blind period (Screening, Month 12), the Viaskin Milk 500 µg open-label period (Month 24, Month 36 and Month 48) and the Viaskin Milk 300 µg open-label period (12 and 24 months after the switch) are provided below. Further details are provided in the Manual of Procedures for the DBPCFC.

Only clear-cut OBJECTIVE immediate-type symptom(s) requiring treatment will be considered a permissible reason to stop the DBPCFC and to determine the eliciting dose (highest dose given during the challenge) and the CRD of cow's milk. For the open-label treatment period with Viaskin Milk 300 µg, abdominal complaints will also be considered as a criterion for stopping the challenge (see below). The main objective symptoms to expect are as follows (this list is not exhaustive; also refer to [Appendix 14.2](#), OFC Symptom Score Sheets^{21, 22}): local or generalized pruritus, flushing, local or generalized urticaria, hives, swollen lips, swollen tongue, throat tightness, vomiting, diarrhea, dyspnea, rhinorrhea, sneezing, wheezing, conjunctivitis, asthma, drop of the PEF, hypoxia, hypotension, hypotonia, decreased level of consciousness associated with collapse and/or incontinence or other life threatening symptoms.

The stopping rules applying for DBPCFCs performed during the double-blind placebo-controlled period and the open-label treatment period with Viaskin Milk 500 µg were the following:

- There is a >1-point rise in an objective symptom from any category in the OFC Symptom Score Sheets, except only for pruritus, which requires >2-point rise
- There is ≥1-point rise in an objective symptom from ≥2 categories in the OFC Symptom Score Sheets
- There is a 1-point rise in an objective symptom from 1 category in the OFC Symptom Score Sheets, with the following exceptions:
 - Pruritus : 0 to 1 or 0 to 2
 - Urticaria: 0 to 1

- Rash: 0 to 1
- Sneezing/Itching: 0 to 1
- Nasal Congestion: 0 to 1
- Rhinorrhea: 0 to 1
- Laryngeal: 0 to 1 (if explained and not persistent)

The stopping rules applying for DBPCFCs performed during the open-label treatment period with Viaskin Milk 300 µg are the following:

Only 1 out of 5 categories has increased its grading symptom score

≥ 1-point rise (i.e. mild, moderate or severe)	OR	≥ 2-point rise (i.e. moderate or severe)	OR	3-point rise (i.e. severe)

 ○ Wheezing ○ Objective Gastrointestinal** ○ Cardiovascular/neurological*** 		
 ○ Urticaria ○ Angioedema ○ Rash 		
 ○ Pruritus ○ Sneezing /Itching ○ Nasal Congestion ○ Rhinorrhea ○ Conjunctivitis ○ Abdominal complaints

2 categories (or more) have increased their grading symptom scores

≥ 1-point rise (i.e. mild, moderate or severe)	AND	≥ 2-point rise (i.e. moderate or severe)

 ○ Urticaria ○ Angioedema ○ Rash ○ Laryngeal* ○ Wheezing ○ Objective Gastrointestinal** ○ Cardiovascular/neurological*** 		
 ○ Pruritus ○ Sneezing/Itching ○ Nasal Congestion ○ Rhinorrhea ○ Conjunctivitis ○ Abdominal complaints

* "Laryngeal" means symptoms due to laryngeal oedema and must be differentiated from another cause of cough like pharyngeal transient irritation or lower respiratory symptoms. Transient laryngeal irritation will not be considered as an objective OFC symptom and will not be considered in the stopping rules.

**For emesis/vomiting, the symptoms may result from two different situations: vomiting/spitting-up during the feeding, resulting from subjective intolerance to the food formula or vomiting/emacsis resulting from a gastrointestinal allergic reaction to the milk allergen, usually delayed from the feeding. Only the second situation will be considered as an objective OFC symptom and will be considered for the stopping rules.

***Cardiovascular symptoms: hypotension or cardiovascular failure directly related to the systemic allergic reaction. They have to be differentiated from similar symptoms related to another cause, such as a dizziness induced by vomiting.

In case of subjective symptoms, eg, mouth pruritus, throat pruritus, nausea, abdominal pain or any other subjective symptoms at a specific dose, deemed significant enough to question whether an objective symptom could occur, the Investigator can, under these conditions, extend the time between the previous dose and the next dose to see how the subject's symptom(s) evolve(s). The same dose can be repeated only once, to check whether the subjective symptom(s) reappear(s) or not and with what intensity, and whether (an) objective symptom(s) now clearly appear(s). If (an) objective

symptom appear(s), that would be the end of the food challenge. If only (a) subjective symptom(s) still persist(s) with no appearance of an objective symptom, the next highest dose is then given to the subject, and the challenge should continue until the appearance of a clear objective symptom, at which time the challenge will be stopped.

Complete information of all reactions (objective and subjective symptoms) that occurred during the DBPCFC will be reported in the eCRF, along with information about the doses of cow's milk proteins or placebo administered, time of dose administration, first time of appearance of each symptom, severity grades of each symptom, time of appearance of each severity grade, and medication(s)/treatment(s) given to the subject to treat these symptoms.

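### Food challenges in the 300 µg open-label period follow a different stopping rule from the challenges used as their baselines, and the SAP text does not allow for it

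*Protocol*

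**What the plan says.** Protocol 7.3.1.1.3 ties the eliciting dose and the CRD to the stopping decision: "Only clear-cut OBJECTIVE immediate-type symptom(s) requiring treatment will be considered a permissible reason to stop the DBPCFC". It adds that in the 300 µg period "abdominal complaints will also be considered as a criterion for stopping the challenge".

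It then sets out two rules.

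- **Earlier rule** (screening, Month 12 and the 500 µg period). A challenge stops on a rise of more than one point in an objective symptom (more than two for pruritus), on a one-point rise in a symptom outside a list of exceptions, or when "There is ≥1-point rise in an objective symptom from ≥2 categories in the OFC Symptom Score Sheets".
- **OL-300 rule** ("The stopping rules applying for DBPCFCs performed during the open-label treatment period with Viaskin Milk" 300 µg). Two tables of symptom-specific thresholds apply. One is headed "Only 1 out of 5 categories has increased its grading symptom score" and the other "2 categories (or more) have increased their grading symptom scores".

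SAP 8.2.1.2 defines OL-300 responders, and SAP 8.2.2.2 summarises OL-300 CRD, change in CRD and improved, stable or deteriorated status. Both use two baselines. The first is the screening challenge. The second is the last challenge before any active treatment, which is Month 12 for subjects randomized to placebo and screening for all others. Neither section mentions the stopping rule.

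SAP 8.2.5.2 and 9.4.2 also summarise symptoms and severity during OL-300 challenges, and 8.2.5.2 uses the worst intensity.

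**The concern.** CRD is the sum of the doses given before the challenge stops. If the stopping threshold moves between baseline and follow-up, CRD can move with no change in the subject. There is no control arm after Month 12 to reveal such a shift.

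The OL-300 challenge summaries bear directly on the third study objective, the therapeutic benefit of the most effective tested dose over 24 months. A reader of those tables would assume that change in CRD compares like with like.

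The severity tables have a related problem. A rule that waits for higher grades also changes the worst grade recorded.

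**Working it through.** **Thresholds side by side** (point rise needed to stop; Protocol 7.3.1.1.3 and Appendix 14.2)

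| Symptom | Alone: earlier | Alone: OL-300 | Two categories: earlier | Two categories: OL-300 |
|---|---|---|---|---|
| Pruritus | 3 | 3 | 1 | 2 |
| Urticaria, rash | 2 | 2 | 1 | 1 |
| Angioedema | 1 or 2* | 2 | 1 | 1 |
| Sneezing/itching, nasal congestion, rhinorrhea | 2 | 3 | 1 | 2 |
| Laryngeal | 1 or 2* | 2† | 1 | 1 |
| Conjunctivitis | 1 | 3 | 1 | 2 |
| Wheezing, objective gastrointestinal, cardiovascular/neurological | 1 | 1 | 1 | 1 |
| Abdominal complaints | none | 3 | none | 2 |

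*Depends on the reading. Angioedema is not in the exception list, but SAP 8.2.5.1 scores it together with urticaria. The laryngeal exception is conditional.
†From Appendix 14.2, because laryngeal is not in the single-category table as extracted.

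Every objective OL-300 threshold is at or above the earlier one. So if categories are read the same way in both rules, no combination of objective symptoms stops an OL-300 challenge that the earlier rule would have continued. Only the abdominal-complaints row works the other way.

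**How many symptom profiles differ.** These are unweighted profiles of grades 1 to 3. They are not patient frequencies, and they ignore the need-for-treatment condition.

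| Profiles | Total | OL-300 stops later | OL-300 stops earlier |
|---|---|---|---|
| One objective symptom (12 × 3) | 36 | 5–7 | 0 |
| Two objective, different categories (50 × 9) | 450 | 25 or 32 | 0 |
| Two objective, same category (16 × 9) | 144 | 26–33 | 0 |
| Abdominal complaints plus one objective symptom outside the gut (11 × 9) | 99 | 6–12 | 9–14 |

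In the second row, 25 applies if any two qualifying symptoms suffice and 32 if one is needed from each column of the two-category table. Ranges cover the starred readings. If the associated-symptom column of Appendix 14.2 also covers two symptoms in the same category, the third row becomes 16–28 later and 2–6 earlier, for example urticaria grade 1 with rash grade 1.

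**What one dose step does.** The doses in Protocol 7.3.1.1.2 cumulate to 1, 4, 14, 44, 144, 444, 1444, 3444 and 6444 mg. The plan's own responder thresholds reproduce: 1 + 3 + 10 + 30 + 100 = 144 and 144 + 300 + 1000 = 1444. Applying the responder definition (at least 10-fold and at least 144 mg, or at least 1444 mg), with full doses and no repeats:

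| Baseline CRD (mg) | Lowest responder CRD (mg) | One step below: non-responder (mg) |
|---|---|---|
| 1, 4, 14 | 144 | 44 |
| 44 | 444 | 144 |
| 144, 444 | 1444 | 444 |

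Step ratios up to 1444 mg run from 444/144 = 3.1 to 4/1 = 4.0. For every baseline possible at screening, a one-step shift at the boundary changes responder status. Baselines of 1444 mg or more, possible only for placebo-randomized subjects under the second definition, need no increase. One extra dose also moves an otherwise stable subject above baseline, unless already at 6444 mg.

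**The case against.** The strongest reply is that little hangs on this. The outputs are descriptive, the challenges are optional, and an uncontrolled before/after comparison could not isolate a treatment effect even under one rule. A changed responder status needs both a discordant symptom profile and a CRD at the boundary, and the documents give a frequency for neither. That stands. It limits the weight of the point, but it does not make the comparison like-for-like.

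The profile counts may also overstate the difference. Of the cross-category pairs that stop later, 17 of 25 (or 20 of 32) are two grade-1 symptoms. Many of these might not have met the need-for-treatment condition at baseline either. That stands too, and the counts show mechanism only.

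Programmed truncation cannot reproduce that condition, the conditional laryngeal exception or investigator judgement. It would be applied at follow-up only, so it probably understates OL-300 CRD. That stands, and the result should be labelled as a bound.

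On the protocol text, a reader might infer that the statement in 7.3.1.1.2 that later challenges follow the screening procedures contradicts the second rule. It does not, because that section refers to 7.3.1.1.3, which assigns rules by period. Section 7.3.1.1.3 also expressly adds abdominal complaints for OL-300. Its closing text, however, has no period limit. It counts abdominal pain as subjective and says that where only subjective symptoms persist, "with no appearance of an objective symptom, the next highest dose is then given to the subject". Appendix 14.2 scores abdominal pain under subjective complaints and carries no period label.

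The Manual of Procedures and the table mock-ups are separate documents and were not available. A caveat could already sit in a table footnote.

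**Conclusion.** The point holds as a limited one. OL-300 CRD, responder and improvement summaries set values from one stopping rule against baselines from another, and the SAP text does not say so. The OL-300 symptom and severity summaries are affected as well.

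The objective-symptom part has a clear direction: at the same point or later, hence CRD the same or higher. This rests on reading categories as the five body systems and on taking the laryngeal threshold from Appendix 14.2. The abdominal-complaints criterion pulls the other way.

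A reader might infer that OL-300 responder rates are inflated. The documents do not support that. They give no symptom frequencies, so the net direction and the number of subjects affected are unknown. A reader might also infer that the main efficacy result is compromised. It is not, because screening and Month 12 share one rule and no OL-300 output is a hypothesis test.

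The change is worth making because it is cheap and leaves the planned analysis in place.

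**What to change.** In the SAP:

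- Keep observed CRD as planned. State the rule change as a caveat with all OL-300 food-challenge tables, including those under 8.2.5.2 and 9.4.2.
- Add one sensitivity analysis to 8.2.1.2 and 8.2.2.2. Truncate each OL-300 milk challenge at the first dose that meets the earlier rule. The data are already required in the eCRF: dose times and "first time of appearance of each symptom, severity grades of each symptom, time of appearance of each severity grade".
- Fix in advance the readings of angioedema, laryngeal grade 1 and the two-category table. Where a challenge stopped only for abdominal complaints and responder status is undetermined, show it both ways.
- Report the number of responder classifications that change, and label the result an approximate, probably conservative bound.
- Correct 8.2.2.2 before counting changed improvement classifications. Improvement and deterioration are both defined there as a follow-up CRD above baseline.

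In the protocol, the general text on subjective symptoms in 7.3.1.1.3 must be reconciled with the OL-300 abdominal-complaints criterion, and Appendix 14.2 should state the period to which its thresholds apply. No view is taken on which stopping rule is right, and the sensitivity analysis does not alter how challenges are conducted.

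The cost is SAP wording, one derivation, and programming and review time. The sponsor may also have to report a less favourable responder rate beside the planned one.

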At the end of the second day of the food challenge (Visit 3), the sequence of the 2 formulas (milk or placebo) administered to the subject will be unblinded by the appropriate unblinded staff (eg, dieticians, study nurses, pharmacists, pharmacy technicians, licensed medical assistants, or any other qualified site personnel, as delegated by the Investigator) and revealed to the medical staff. The results of the challenge will then be established and recorded in the eCRF as follows:

1. The subject had objective symptoms to the placebo formula at any dose leading to stopping the challenge. S/He cannot be randomized in the study.
2. The subject had no objective symptoms during the 2 days of the DBPCFC, neither to the placebo nor to the milk formula, even at the highest dose of 300 mg of cow's milk proteins. S/He is considered not allergic enough to cow's milk to participate in this study and cannot be randomized in the study.
3. The subject had no objective symptom when receiving placebo but had an objective reaction (as defined in [Section 7.3.1.1.3](#)) at 1 of the doses of the milk formula consumed between 1 mg and 300 mg inclusive. S/He will be randomized in the study as s/he reacted to a dose of milk proteins lower than or equal to 300 mg (eliciting dose).

7.3.1.1.2 DBPCFC at Month 12 (Visits 12 and 13), Month 24 (Visits 16 and 17), Month 36 (Visits 19 and 20), and Month 48 (Visits 22 and 23), and optional DBPCFC after 12 months (Visits S3 and S4) and 24 months (Visits S6 and S7) of treatment with Viaskin Milk 300 µg

No patch should be applied on the day of the DBPCFC until all DBPCFC procedures have been completed.

Following results of the 12-month blinded period, the DBPCFCs that were to be performed at Month 24, Month 36 and Month 48 should not be conducted while the subjects are still receiving Viaskin Milk 500 µg.

After subjects switch to Viaskin Milk 300 µg, the DBPCFCs at 12 months and 24 months will be optional and left at the Investigator's and the subject's decision. However, if a subject experienced a severe anaphylaxis to cow's milk during the MILES study, whether or not occurring during the DBPCFC, no further DBPCFC should be conducted for this subject.

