All DBPCFCs at Month 12 and forward will be conducted using the same procedures that are described for the screening DBPCFC, with the exception that the dosing will continue beyond the 300 mg dose of cow's milk proteins if there are no objective symptoms (see [Section 7.3.1.1.3](#)) at the 300 mg dose. The challenge must be continued up to the last dose of 3000 mg of cow's milk proteins or until an objective reaction occurs (as defined in [Section 7.3.1.1.3](#)).

For all DBPCFCs at Month 12 and forward, the doses of cow's milk proteins will be 1 mg, 3 mg, 10 mg, 30 mg, 100 mg, 300 mg, 1000 mg, 2000 mg, and 3000 mg administered at 20-minute intervals. The Investigator may use clinical judgment to increase the intervals between doses in case there is a suspicion that an objective reaction may be developing (see [Section 7.3.1.1.3](#)). Very occasionally, the Investigator may use clinical judgment to repeat the same dose (only once) before administration of the next higher dose and only if there is a suspicion that an objective reaction may be developing (see [Section 7.3.1.1.3](#)). The dose and time of administration of each dose (and of a repeated dose when applicable) will be recorded in the eCRF. The subjects

will be kept under observation for an additional 3 hours after the ingestion of the last dose of the challenge formula.

Subjects should undergo both days of the DBPCFC (milk and placebo). However, in exceptional cases, the DBPCFC on the second day of the challenge might not be performed if the subject had a severe anaphylactic reaction during the first day of the challenge, leaving no doubt about the nature of the formula administered, ie, cow's milk. In this rare case and in this case only, the formula will be unblinded to confirm that the subject effectively received the milk formula. A severe anaphylactic reaction would involve a >20% drop of blood pressure, cyanosis or SpO₂<92%, confusion, collapse, loss of consciousness, 3 doses of epinephrine or more (see [Appendix 14.4](#)).

At the end of the second day of the food challenge, the sequence of the 2 formulas (milk or placebo) administered will be unblinded by the appropriate unblinded staff (eg, dieticians, study nurses, pharmacists, pharmacy technicians, licensed medical assistants, or any other qualified site personnel, as delegated by the Investigator) and revealed to the medical staff. The results of the challenge will then be established and recorded in the eCRF.

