14.2 Oral Food Challenge Symptom Score Sheets

I. SKIN

		Stopping rules: # of grade increase	
		Alone	Associated
A. Pruritus		+3	+2
0 = Absent			
1 = Mild: occasional scratching			
2 = Moderate: scratching continuously for >2 minutes at a time			
3 = Severe: hard continuous scratching excoriations			
B. Urticaria		+2	+1
0 = Absent			
1 = Mild: ≤3 hives			
2 = Moderate: <10 hives but >3			
3 = Severe: generalized involvement			
C. Angioedema		+2	+1
0 = Absent			
1 = Mild: mild lip edema			
2 = Moderate: significant lip or face edema			
3 = Severe: generalized involvement			
D. Erythematous Rash		+2	+1
0 = Absent			
1 = Mild: few areas of faint erythema			
2 = Moderate: areas of erythema (>20% and <50%), macular and raised rash			
3 = Severe: generalized marked erythema (>50%), extensive raised lesions (>25%)			
Erythematous Rash % area involved (see below):		/ _____	/ _____ /%

	1-4 years old	5-8 years old	9-12 years old	≥13 years old
Head	17%	16%	12%	4.5%
Neck	2%	2%	2%	1%
Anterior trunk	16%	14%	14%	18%
Posterior trunk	16%	18%	18%	18%
Leg (1)	15%	15%	17%	18%
Arm (1)	9.5%	10%	10%	9%

Adapted from Lund CC, Browder NC (1944) The estimation of areas of burns. *Surg Gynecol Obstet* 79: 352-8

II. UPPER RESPIRATORY/OCCULAR

	Stopping rules: minimal # of grade increase	
	Alone	Associated
A. Sneezing/Itching	+3	+2
0 = Absent		
1 = Mild: rare bursts		
2 = Moderate: bursts <10, intermittent rubbing of nose / eyes / external ear canals		
3 = Severe: continuous rubbing of nose / eyes, periocular swelling and/or long bursts of sneezing		
B. Nasal Congestion	+3	+2
0 = Absent		
1 = Mild: some hindrance to breathing		
2 = Moderate: nostrils feel blocked, breathing through mouth most of time		
3 = Severe: nostrils occluded		

C. Rhinorrhea	+3	+2
0 = Absent		
1 = Mild: occasional sniffing		
2 = Moderate: frequent sniffing, requires tissues		
3 = Severe: nose runs freely despite sniffing and tissues		
D. Laryngeal (only symptoms due to laryngeal edema)	+2	+1
0 = Absent		
1 = Mild: throat clearing, occasional cough		
2 = Moderate: hoarseness, frequent dry cough		
3 = Severe: inspiratory stridor		
E. Conjunctivitis (see example below)	+3	+2
0 = Absent		
1 = Mild:		
2 = Moderate:		
3 = Severe:		

Grade 1 Grade 2 Grade 3

III. LOWER RESPIRATORY

	Stopping rules: minimal # of grade increase	
	Alone	Associated
A. Wheezing (including cough due to bronchospasm)	+1	+1
0 = Absent		
1 = Mild: expiratory wheezing to auscultation		

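### The OL-300 stopping table has no threshold for an isolated laryngeal reaction, Appendix 14.2 sets a 2-point rise, and nothing says which governs

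*Protocol*

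**What the plan says.** Protocol 7.3.1.1.3 sets separate rules for the last open-label period: "The stopping rules applying for DBPCFCs performed during the open-label treatment period with Viaskin Milk 300 µg are the following". Two tables follow.

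- The first covers the case "Only 1 out of 5 categories has increased its grading symptom score". It has three columns, for rises of at least 1 point, at least 2 points, and 3 points. Laryngeal is in none of them.
- The second covers two or more categories. It lists Laryngeal at a rise of at least 1 point. Its footnote restricts the item to laryngeal oedema and adds: "Transient laryngeal irritation will not be considered as an objective OFC symptom and will not be considered in the stopping rules". It gives no threshold for a laryngeal symptom on its own.

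The score sheets in Appendix 14.2 carry stopping columns for a symptom alone and for a symptom associated with others. Laryngeal is +2 alone and +1 associated. Grade 2 is hoarseness with frequent dry cough; grade 3 is inspiratory stridor.

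For the double-blind and 500 µg periods, the same section used a different rule: "There is a >1-point rise in an objective symptom from any category in the OFC Symptom Score Sheets, except only for pruritus". That rule covers an isolated laryngeal rise of 2 points or more.

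Section 7.3.1.1.2 makes continued dosing mandatory: "The challenge must be continued up to the last dose of 3000 mg of cow's milk proteins or until an objective reaction occurs". It refers to 7.3.1.1.3 for what counts as such a reaction. It also says that after the switch "the DBPCFCs at 12 months and 24 months will be optional and left at the Investigator's and the subject's decision".

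**The concern.** A stopping rule for a paediatric food challenge should cover every graded symptom, and airway signs above all. Here the text that tells sites to keep dosing points to a table in which an isolated laryngeal reaction has no threshold. The appendix does give one. A site that works from the table alone could give the next milk dose to a child with isolated grade 2 or 3 laryngeal oedema. The same table stops a challenge for one episode of emesis.

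The data are affected too. The CRD is the sum of doses given, so a further dose moves the child up the ladder and may change OL-300 responder status. Two sites that follow different texts would record different CRDs for the same reaction.

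**Working it through.** **Step 1. Thresholds side by side** (minimum rise in grade; Protocol 7.3.1.1.3 against Appendix 14.2).

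| Symptoms | Single-category table | Appendix, alone | Two-category table | Appendix, associated |
|---|---|---|---|---|
| Wheezing; objective gastrointestinal; cardiovascular/neurologic (3) | 1 | 1 | 1 | 1 |
| Urticaria; angioedema; rash (3) | 2 | 2 | 1 | 1 |
| Pruritus; sneezing/itching; nasal congestion; rhinorrhea; conjunctivitis; abdominal (subjective) complaints (6) | 3 | 3 | 2 | 2 |
| Laryngeal (1) | none | 2 | 1 | 1 |

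Alone: 3 + 3 + 6 = 12 of 13 agree. Associated: 13 of 13 agree. Total: 12 + 13 = 25 of 26. Laryngeal alone is the only gap.

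**Step 2. Omission or choice?** The 1-point column of the two-category table is the single-category 2-point list followed by the single-category 1-point list, with Laryngeal between them, directly after rash. The single-category table carries the footnote marks for the gastrointestinal and cardiovascular items but not the laryngeal one. Both facts suggest that Laryngeal dropped out of the 2-point column. No rationale is given for leaving it out.

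**Step 3. Which text governs?** Section 7.3.1.1.2 ties the end of dosing to 7.3.1.1.3 and does not mention the appendix there. Section 7.3.1.1.3 cites Appendix 14.2 to complete a list of expected symptoms, and the visit sections cite it for grading. No sentence ranks one against the other.

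**Step 4. What the table does as written.** An isolated laryngeal rise of 2 or 3 points meets no threshold. A 1-point isolated rise stops under neither OL-300 text, so the conflict concerns grades 2 and 3 only. Appendix 14.2 places Laryngeal within its upper respiratory/ocular category. Stridor with grade 2 rhinorrhea is therefore still a rise in one category, and it too meets no single-category threshold.

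**Step 5. Effect on the CRD.** Doses (7.3.1.1.2): 1, 3, 10, 30, 100, 300, 1000, 2000, 3000 mg. With full doses and no repeats:

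- Cumulative doses: 1, 4, 14, 44, 144, 444, 1444, 3444, 6444 mg.
- Ratio of each value to the one before: 4.00, 3.50, 3.14, 3.27, 3.08, 3.25, 2.39, 1.87.

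**Step 6. Effect on responder status.** SAP 8.2.1.2 calls a subject a responder if the CRD is at least 1444 mg, or is at least 10 times baseline and at least 144 mg. The screening ladder stops at 300 mg, so the screening CRD can take six values.

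| Screening CRD (mg) | 10-fold (mg) | First CRD that qualifies (mg) | Step that changes status (mg) |
|---|---|---|---|
| 1 | 10 | 144 | 44 to 144 |
| 4 | 40 | 144 | 44 to 144 |
| 14 | 140 | 144 | 44 to 144 |
| 44 | 440 | 444 | 144 to 444 |
| 144 | 1440 | 1444 | 444 to 1444 |
| 444 | 4440 | 1444 (absolute criterion) | 444 to 1444 |

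For each baseline, exactly one of the eight steps changes a non-responder into a responder.

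**The case against.** The strongest reply is that the protocol does supply the number. The columns in Appendix 14.2 are labelled as stopping rules, every OL-300 challenge is graded on those sheets, and the body table is silent rather than contradictory. The person grading the larynx has +2 on the page.

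The rest of 7.3.1.1.3 also points towards stopping. It treats clear objective symptoms needing treatment as grounds to stop and names throat tightness and dyspnea among them. The laryngeal footnote excludes only transient irritation. Appendix 14.4 places hoarseness and stridor under moderate anaphylaxis, and challenges run under direct medical supervision. The Manual of Procedures, which sites must use, is not available here and may carry the threshold. A table bullet may also have been lost when the PDF was read.

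Most of this stands, and it lowers the chance of harm. Many investigators would stop. A lost bullet is unlikely, because the three lists look intact and Laryngeal survives in the adjacent table, but it cannot be excluded.

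None of it closes the gap. No text puts the appendix above the table, and the mandatory-dosing sentence points to the section that contains the table. The sentence in 7.3.1.1.3 that ends a challenge at a clear objective symptom concerns the follow-up of subjective symptoms. Read as a general rule, it would contradict the tables, which let grade 1 urticaria or rash alone continue.

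**Conclusion.** The concern holds. The OL-300 single-category table gives no threshold for Laryngeal, Appendix 14.2 gives +2 alone, and the protocol does not say which applies. An accidental omission with +2 intended is the likely reading. Applied as written, the table is less protective for an airway sign than the rule used in the double-blind and 500 µg periods.

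Per affected challenge, one extra full dose multiplies the CRD by 3.1 to 4.0 up to 1444 mg, by 2.4 from 1444 to 3444 mg, and by 1.9 from 3444 to 6444 mg. It changes responder status only at the single step shown for each baseline. These figures assume full doses, no repeats, and that the further dose is actually given. The documents give no frequency of isolated grade 2 or 3 laryngeal reactions, so nothing is claimed about the overall responder rate.

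The scope is narrow: optional challenges, summarised descriptively. The Month 12 primary endpoint used the earlier rules and is unaffected. The point should be corrected, mainly for safety. Confidence is medium because the original table and the Manual of Procedures have not been seen.

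**What to change.** 1. Check the table in the original PDF of the protocol.
2. If Laryngeal is absent there, add it with its footnote mark to the 2-point column of the single-category table in 7.3.1.1.3. All 26 thresholds then agree with Appendix 14.2.
3. Send sites a clarification letter, and confirm that the Manual of Procedures states the same threshold.
4. If OL-300 challenges have already taken place, list those with an isolated laryngeal rise of 2 points or more followed by a further dose. Under 7.3.1.1.3 the eCRF records doses, symptom grades and their times, so these cases can be found.

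The cost is one table entry and one letter, plus a data listing if step 4 applies. No analysis changes.
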